### 4.4. Pregnancy and Breastfeeding Restrictions / Contraception Requirements

TTR transports vitamin A in plasma; therefore, reductions in circulating vitamin A levels accompany reductions in TTR caused by patisiran. Vitamin A deficiency has known effects on both male and female reproductive performance and embryo/fetal development. It is not known whether decreased levels of vitamin A at efficacious patisiran doses in ATTR patients who are male or who are women of child bearing potential will affect reproduction. Histopathological evaluations of all of the reproductive organs have been conducted in the rat and non-human primate (NHP) toxicology studies including a chronic NHP study in sexually mature animals, where there were no adverse effects in males (including sperm analyses and spermatogenic staging) or females. In a dose range-finding rat embryo/fetal development study

conducted with patisiran, there were no effects on mating, fertility, ovarian or uterine parameters, or fetal development despite reductions (-88% from baseline) in serum vitamin A in the dams dosed with the rat-specific TTR surrogate siRNA.

Women of child-bearing potential are defined as any woman or adolescent who has begun menstruation. A post-menopausal woman is defined as a woman who has 12 months of spontaneous amenorrhea or 6 months of spontaneous amenorrhea with serum FSH levels >40 mIU/mL or 6 weeks postsurgical bilateral oophorectomy with or without hysterectomy.

In this study, women of child-bearing potential must have a negative pregnancy test, cannot be breastfeeding, and must be using 2 highly effective methods of contraception prior to dosing on Day 0, throughout study participation, and for 75 days after last dose of patisiran in this study. Highly effective methods of birth control result in a low failure rate (ie, less than 1% per year). Acceptable forms of effective contraception are defined as follows:

- Hormonal: established use of oral, implantable, injectable, or transdermal hormonal methods of conception
- Placement of an intrauterine device (IUD)
- Placement of an intrauterine system (IUS)
- Mechanical/barrier method of contraception: condom or occlusive cap (diaphragm or cervical/vault cap) in conjunction with spermicide (foam, gel, film, cream or suppository)

Note: Failure rates indicate that, when used alone, the diaphragm and condom are not highly effective forms of contraception. Therefore the use of additional spermicides does confer additional theoretical contraceptive protection. However, spermicides alone are inefficient at preventing pregnancy when the whole ejaculate is spilled. Therefore, spermicides are not a barrier method of contraception and should not be used alone.

- Surgical sterilization of male partner (with the appropriate post-vasectomy documentation of the absence of sperm in the ejaculate; for female patients on the study, the vasectomized male partner should be the sole partner for that patient);
- Sexual true abstinence: when this is in line with the preferred and usual lifestyle of the patient. Periodic abstinence (eg, calendar, ovulation, symptothermal, post-ovulation methods) and withdrawal are not acceptable methods of contraception.

Patients should be instructed to use 2 different forms of effective contraception from the list above. Examples of 2 forms of highly effective contraception are as follows:

- Oral, implantable, injectable, or transdermal contraceptives in conjunction with condom or diaphragm and spermicide
- IUD in conjunction with condom or diaphragm and spermicide
- Surgical sterilization of partner in conjunction with condom or diaphragm and spermicide

Interaction between patisiran and hormonal contraceptives is not anticipated. The patisiran drug substance ALN-18328 (siRNA), and the 2 novel lipid excipients 1,2-Dilinoleyloxy-N,N-dimethylpropylamine (DLin-MC3-DMA) and (R)-methoxy-PEG2000-carbamoyl-di-O-myristyl-sn-glyceride (PEG-2000-C-DMG), were evaluated by in vitro human microsomal incubations to determine if any had inhibitory effects on cytochrome P450 (CYP) activity. None of the components displayed an inhibitory effect on any of the CYPs investigated (CYP1A2, CYP2C9, CYP2C19, CYP2D6 and CYP3A4/5). In addition, there was no induction of CYP1A2, CYP2B6, or CYP3A4 at any of the concentrations studied. These data suggest a low likelihood of patisiran to interfere with the metabolism of hormonal contraceptives.

Males (including men who have had vasectomies) with partners of child-bearing potential, must agree to use 1 barrier method (eg, condom) and 1 additional method (eg, spermicidal foam, gel, film, cream, or suppository) of contraception throughout study participation and for 75 days (ie, a whole spermatogenic cycle) after the last dose of patisiran in this study. Males must also abstain from sperm donation after the first dose of patisiran through study participation and for 75 days after last dose of patisiran in this study.

In Japan it is recommended that the Investigators select appropriate contraception methods, as available.

Pregnancy reporting guidelines are provided in Section [9.5.2](#).

## 5. TREATMENT OF PATIENTS

### 5.1. Description of Study Drug

Patisiran Solution for Injection is a ribonucleic acid interference (RNAi) therapeutic consisting of an siRNA targeting TTR messenger RNA (mRNA) formulated in a LNP. The patisiran drug product is a sterile formulation of ALN-18328, an siRNA targeting TTR, formulated as LNPs siRNA with lipid excipients (DLin-MC3-DMA, 1,2-Distearoyl-sn-glycero-3-phosphocholine [DSPC], cholesterol, and PEG2000-C-DMG in isotonic phosphate buffered saline. Patisiran Solution for Injection contains 2 mg/mL of the TTR siRNA drug substance.

### 5.2. Concomitant Medications

Use of the following medications/treatments is prohibited during study participation:

- Any investigational agent other than patisiran
- Corticosteroids other than those administered as premedications prior to the dose of patisiran, those used to treat an infusion reaction, or topical or inhaled corticosteroids. However, for patients with chronic inflammatory disorders (eg, asthma, rheumatoid arthritis), systemically administered steroids may be permitted provided that: 1) the dose is <20 mg/day prednisone or equivalent if administered chronically, or 2) for doses ≥20 mg/day, administration is limited to no more than 5 consecutive days.

Use of the medications/treatments listed below is permitted in patients who were already taking such medications while on the parent study in accordance with the rules of that study protocol. For patients who did not take these medications while on the parent study, use of these medications is permitted, if necessary, only after the patient has completed the 52-week visit.

- Tafamidis
- Diflunisal
- Doxycycline/TUDCA

Medications and treatments other than those specified above, including palliative and supportive care approved by the Investigator for disease-related symptoms, are permitted during the study.

All patients will be asked to continue to take the recommended daily allowance of vitamin A. Patients will receive this daily dose for the duration of their participation in the study while being administered patisiran. In Japan, the clinical sites will provide patients with a prescription for vitamin A.

Any concomitant medication or treatment that is required for the patient's welfare may be given by the Investigator. Use of all concomitant medications and treatments will be recorded on the patient's CRF through the end of the patient's participation in the study. This will include all prescription drugs, herbal preparations, over-the-counter (OTC) medications, vitamins, and minerals. Any changes in medications during the study will also be recorded on the CRF. Similarly, concomitant medications that continue from the parent study will be entered into the database.

### **5.3. Treatment Compliance**

Compliance with patisiran administration is dependent on the proper preparation and administration of IV infusions by trained personnel and attendance by the patient at the clinic for scheduled assessment visits. Compliance with patisiran administration will be verified through observation by study staff or (in applicable regions) trained home healthcare professionals. A dose will be considered completed if 80% or more of the total volume of the IV solution was administered to the patient. Patients will be permitted to miss an occasional dose of patisiran; however, if a patient misses 3 consecutive doses, the Investigator, in consultation with the Medical Monitor, will discuss whether the patient will be able to continue on the study.

### **5.4. Randomization and Blinding**

This is an open-label study; however, patients rolling over into this study from a previously blinded study will remain blind to their previous treatment assignment until database lock has occurred in that study.

## 6. STUDY DRUG MATERIALS AND MANAGEMENT

### 6.1. Study Drug Packaging and Labeling

All packaging, labeling, and the preparation of patisiran will be in compliance with Good Manufacturing Practice (GMP) specifications, as described in the Manufacture of Investigational Medicinal Products Volume 4 Annex 13, and any other or local applicable regulations.

Patisiran labels will include all appropriate local labeling requirements on the vial and external label. Sample labels will be submitted to health authorities, per local country submission requirements.

The patisiran drug product is packaged in 10 mL glass vials with a fill volume of 5.5 mL. The container closure system consists of a United States Pharmacopeia/European Pharmacopoeia (USP/EP) Type I borosilicate glass vial, a Teflon-faced butyl rubber stopper, and an aluminium flip-off cap.

### 6.2. Study Drug Storage

Patisiran will be stored upright and refrigerated at approximately  $5 \pm 3^{\circ}\text{C}$ . Any deviation from the recommended storage conditions must be reported to the CRO and/or the Sponsor and use of the patisiran halted until authorization for its continued use has been given by the Sponsor or designee.

No special procedures for the safe handling of patisiran are required. A Sponsor representative or designee will be permitted, upon request, to audit the supplies, storage, dispensing procedures, and records.

Patisiran supplied for this study may not be administered to any person not enrolled in the study.

### 6.3. Study Drug Preparation

Staff at each clinical site or the healthcare professional administering patisiran will be responsible for preparation of patisiran doses, according to procedures detailed in the Pharmacy Manual.

All patients in this study will receive 0.3 mg/kg patisiran once every 21 days ( $\pm 3$  days). The amount (mg) of patisiran to be administered will be based on the patient's body weight (kg). For each dose administered, the weight obtained during the previous dosing visit will be used to calculate the dose of patisiran. In the event that the weight obtained on the previous dosing day is not available, the weight obtained pre-dose on the current dosing day can be used for dose calculation. Patients who weigh 105 kg or more will receive patisiran dosing based on an assumption of a body weight of 104 kg.

Patisiran will be prepared under aseptic conditions. The total amount to be infused into each patient at each dosing visit will be 200 mL. Sterile normal saline (0.9% NaCl) will be added to a sterile infusion bag, and the calculated volume of patisiran will be withdrawn from the vials and injected into the infusion bag.

## 6.4. Administration

### 6.4.1. Premedication

Prior to each dose of patisiran, patients will receive the following premedications in order to reduce the risk of experiencing an IRR at least 60 minutes before the infusion:

- Intravenous dexamethasone (10 mg) or equivalent
- Oral paracetamol/acetaminophen (500 mg) or equivalent
- Intravenous H2 blocker (ranitidine 50 mg, famotidine 20 mg, or equivalent other H2 blocker dose)
- Intravenous H1 blocker: diphenhydramine 50 mg (or equivalent other IV H1 blocker available at the clinical site). Hydroxyzine 25 mg per os (PO, orally) or fexofenadine 30 mg or 60 mg PO or cetirizine 10 mg PO may be substituted for any patient who does not tolerate IV diphenhydramine or other IV H1 blocker.

Further details (including a table of equivalent premedications) can be found in the patisiran Pharmacy Manual.

Patients will be started on the above premedication regimen. However, modifications may be made to the premedication regimen after consultation with the medical monitor either due to a patient's inability to tolerate one or more of the premedications or to the occurrence of IRRs unresponsive to slowing of the infusion rate.

- If a patient is having difficulty tolerating the steroid premedication regimen (e.g., patient develops uncontrolled hyperglycemia, altered mental status, or other complication), then lowering of the steroid premedication may be allowed for that patient after consultation with the medical monitor.
- If after consultation with the medical monitor, it is agreed that an individual patient's steroid premedication will be lowered, then the following steps **must be followed**:
  - 1) If the current steroid dosage is 10 mg or less of intravenous dexamethasone or equivalent, then the patient may be lowered in increments no greater than 2.5 mg intravenous dexamethasone or equivalent.
  - 2) After each incremental lowering of intravenous dexamethasone or equivalent, the patient must receive three consecutive intravenous doses of patisiran without IRR and continued signs or symptoms of steroid intolerance before further reductions in steroid premedications.
  - 3) The premedication steroid dosage should not be reduced below 5 mg intravenous dexamethasone or equivalent.

Alternatively if a patient experiences an IRR when 10 mg or less of IV dexamethasone or equivalent is used as the steroid premedication, then proceed to Section 6.4.3.

If a patient's premedication regimen was modified prior to enrollment in Study TTR02-006, the patient may continue on that modified premedication regimen.

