**Duration of treatment:**

The duration of the study has been determined to allow the collection of long-term safety, tolerability and efficacy data of patisiran in patients with FAP who have completed a prior study with patisiran. The estimated duration of the study is 5 years.

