In addition, after consultation with the medical monitor, specified patients who are intolerant of 10 mg IV dexamethasone or equivalent on the day of infusion may be considered for further step-wise reduction in dexamethasone or equivalent as specified in the protocol (See Protocol Section 6.4.1). Alternatively, after consultation with the medical monitor, if the patient develops infusion related reactions on 10 mg IV or less of dexamethasone, even after slowing of the infusion, that patient will be allowed to increase the steroid premeditation dose in a step-wise manner as indicated per protocol (See Protocol Section 6.4.3).

Clarification of Risk Benefit Assessment

The risk benefit assessment has been updated to reflect liver function test abnormalities and risk for osteoporosis. Because patients with FAP may be at risk for osteoporosis, it has been added that, if there is no medical contraindication, and per investigator judgment and local standard of care, study

participants should, if appropriate, receive therapy for the prevention and early treatment of osteoporosis such as: calcium and vitamin D supplementation, bisphosphonates, calcitonin, parathyroid hormone, estrogen agonist/antagonist or combination therapies.

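### Read literally, step 2 of the mandatory steroid step-down in 6.4.1 bars a further reduction for a patient who is still steroid-intolerant, although intolerance is the ground for lowering the dose

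*Protocol*

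**What the plan says.** Section 6.4.1 starts patients on 10 mg of intravenous dexamethasone or equivalent before each patisiran infusion. The ground for lowering it is stated first: "If a patient is having difficulty tolerating the steroid premedication regimen", "then lowering of the steroid premedication may be allowed for that patient after consultation with the medical monitor". The examples given are uncontrolled hyperglycemia and altered mental status.

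Once lowering has been agreed with the medical monitor, three steps become mandatory, and the protocol sets that requirement in bold:

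- Step 1, for a current dose of 10 mg or less: "the patient may be lowered in increments no greater than 2.5 mg intravenous dexamethasone or equivalent".
- Step 2, after each reduction: "the patient must receive three consecutive intravenous doses of patisiran without IRR and continued signs or symptoms of steroid intolerance before further reductions".
- Step 3: "The premedication steroid dosage should not be reduced below 5 mg intravenous dexamethasone or equivalent".

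IRRs on 10 mg or less are sent to section 6.4.3, where the steroid is increased or returned to an earlier dose. The steps there are recommended, not mandatory. Step 2 has the same wording in the current global version (3.0) and in the Argentina version (3.1).

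**The concern.** In step 2 a single 'without' is followed by two nouns joined by 'and'. No comma, verb or second preposition separates them. The plain grammatical reading is three doses with neither an IRR nor continuing intolerance. On that reading the rule works against its purpose: the patient whose intolerance has resolved qualifies for the next reduction, and the patient who is still intolerant does not.

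At stake is the handling of an individual patient with, say, continuing uncontrolled hyperglycemia at 7.5 mg. A site that follows the words would hold the dose, and one that follows the purpose would lower it. Section 1.4 of the protocol itself treats repeated glucocorticoid exposure as a risk, through bone mineralization. The point concerns dosing safety and consistency between sites, not statistical inference.

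**Working it through.** The protocol gives no figure to reproduce. The check compares the two readings with the rest of the section and then sizes the consequence.

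**The two readings**

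| Status after three doses at the reduced level | (a) 'without' covers both terms | (b) no IRR, intolerance persisting |
|---|---|---|
| No IRR, still intolerant | not reducible | reducible |
| No IRR, intolerance resolved | reducible | not reducible |
| IRR occurred | not reducible | not reducible |

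Reading (b) fits the ground for lowering in 6.4.1. It also fits the Amendment 1 rationale, used here only as evidence of intent, under which "specified patients who are intolerant of 10 mg IV dexamethasone or equivalent on the day of infusion may be considered for further step-wise reduction". Reading (a) fits the sentence as punctuated. Nothing else in the protocol settles the choice.

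**Inputs**

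- Starting dose 10 mg, maximum decrement 2.5 mg, floor 5 mg, three doses between reductions (6.4.1).
- Dosing every 21 (±3) days (6.3, 6.4.2).
- Duration: "The estimated duration of the study is 5 years" (Synopsis, Duration of treatment).

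**How often step 2 applies**

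- Minimum number of reductions from 10 to 5 mg: (10 − 5) / 2.5 = 2. Step 2 does not apply to the first, so it applies to 2 − 1 = 1, the move from 7.5 to 5 mg.
- With smaller steps of 1.25 mg (an assumption): (10 − 5) / 1.25 = 4 reductions, of which 3 fall under step 2.
- Every route from 10 mg to the floor therefore passes through step 2 at least once.
- Earliest first dose at 5 mg: 3 × 21 = 63 days after the first dose at 7.5 mg (54 to 72 days if each interval is 18 to 24 days).

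**Excess steroid if a patient is held at 7.5 mg**

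- Infusions per year: 365.25 / 21 = 17.39.
- At 7.5 mg: 17.39 × 7.5 = 130.4 mg per year. At 5 mg: 17.39 × 5 = 87.0 mg per year.
- Difference: (365.25 / 21) × 2.5 = 43.5 mg per year (43.48 before rounding).
- Infusions in 5 years: 5 × 365.25 / 21 = 86.96.
- At least one dose at 10 mg and three at 7.5 mg are given whichever reading applies, so they contribute no difference.
- Ceiling: (86.96 − 4) × 2.5 = 207.4 mg, about 207 mg.

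**The case against.** The strongest reply is that context already resolves the sentence. Intolerance is the reason for lowering, stated in the bullet above the steps, and continued symptoms make sense as the reason to go further. The medical monitor must agree before any lowering starts, so a still-intolerant patient stays at 7.5 mg only if the monitor also adopts the reading that defeats the section. Other provisions protect the patient: treatment needed for welfare is permitted (5.2), poorly controlled diabetes is excluded at entry (4.2), withdrawal for an intolerable adverse event is possible (4.3), and a regimen modified before enrollment may be continued (end of 6.4.1). The Pharmacy Manual, to which 6.4.1 refers for further details, is not available and might address step-down.

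Most of this stands, and it keeps the point small. It does not remove it. The steps are mandatory, 6.4.1 gives no express discretion to waive step 2, and a binding dosing rule should not depend on readers setting its grammar aside.

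Three stronger inferences are not supported:

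- A reader might infer that the protocol definitely forbids the reduction. It does not, because reading (b) is available and more likely intended.
- A reader might infer that, on the literal reading, only a patient who no longer needs a reduction can have one. Step 2 does not say that the three doses must immediately precede the reduction, so a patient with three clean doses whose intolerance later recurs would qualify.
- A reader might multiply the yearly difference by 5 and arrive at 86.96 × 2.5 = 217 mg. That counts the four doses common to both courses.

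**Conclusion.** The point holds as a wording defect in a mandatory safety step. Taken literally, step 2 stops a patient who remains intolerant at 7.5 mg from reaching the dose step 3 permits, contrary to the only ground 6.4.1 gives for lowering the steroid. The probable intent is clear enough, and the monitor's role makes a lasting effect unlikely.

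The size is about 43 mg of dexamethasone per year for a patient held at 7.5 mg. The ceiling of about 207 mg over 5 years assumes full 2.5 mg steps, a first reduction after a single dose at 10 mg, no missed doses, intolerance throughout, and no clarification from the monitor in all that time. The number of patients affected is unknown. No endpoint, analysis or statistical figure depends on this sentence, so the correction is desirable but not urgent.

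**What to change.** Reword step 2 along these lines:

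*Following each reduction, three patisiran infusions in a row must be completed with no IRR. If steroid intolerance is still present, or returns, a further reduction may then be made.*

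The new sentence should not restate the 2.5 mg limit. Step 1 applies that limit only at current doses of 10 mg or less, whereas 6.4.3 allows higher doses; repeating it in step 2 would extend the cap to patients it does not now cover. Leave the step 1 increment limit, the 5 mg floor and section 6.4.3 unchanged.

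The cost is one sentence at the next amendment, in section 6.4.1 of both the global and the Argentina versions. No new data are needed, and the requirement for three doses free of IRR is preserved.

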## 6.4.2. Study Drug Administration

Patisiran will be administered under the supervision of the site personnel every 21 ( $\pm$ 3) days. Patients who have received at least 3 doses of patisiran on this study at the clinical site with no evidence of IRRs or other adverse effects may have patisiran administered at home, where applicable country and local regulations allow. Home administration of patisiran will be done by a healthcare professional trained on the protocol and delivery of premedications and patisiran.

On all dosing days, patisiran will be administered as a 70-minute IV infusion (approximately 1 mL/minute for the first 15 minutes followed by approximately 3 mL/minute for the remainder of the infusion).

- If the patient experiences an IRR the infusion time may be extended up to 3 hours in the event of a mild or moderate IRR.
  - 1) If the patient experiences a mild or moderate IRR that resolves by slowing the infusion rate then no further premedication changes are recommended.
  - 2) If the patient experiences a severe IRR, then patisiran administration will not be resumed until the case is discussed with the Medical Monitor (see Section 6.4.3).
- If the infusion time for a patient was already extended on the parent study due to an IRR, that modified infusion duration may be continued on this study for that particular patient. Returning the patient's infusion duration to 70 minutes will require a discussion with the Medical Monitor.
- For the first 3 infusions of patisiran on this study, the patient's infusion site should be assessed for signs of any localized reaction during the infusion and for 30 minutes after the end of the infusion, and the patient will remain at the clinical site for 1 hour following completion of dosing.

If a patient does not receive a dose of patisiran within the dosing window ( $\pm$ 3 days), the dose will be considered missed and not administered.

Additional details can be found in the patisiran Pharmacy Manual.

In addition to study treatment, patients will receive the recommended daily allowance of vitamin A. Patients will receive this daily dose for the duration of their participation in the study while being administered patisiran. In Japan the clinical sites will provide the subjects with a prescription for vitamin A.

